## **5. ELIGIBILITY-INCLUSION/EXCLUSION**

### **Key Inclusion Criteria:**

1. Eligible patients with atrial fibrillation at enrollment or two or more episodes of atrial fibrillation or flutter, as documented by electrocardiography, at least 2 weeks apart in the 12 months before enrollment
2. Age 18–84
3. On anticoagulation for 6 months prior to enrollment at a stable dose.
4. Willingness to participate in the study and ability to sign informed consent
5. Minimum CAC score of 10

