## **13. STATISTICAL CONSIDERATIONS**

### Statistical analysis

All analyses will be performed on a full analysis set basis (those who stay in the trial to the follow up scan). For the primary analysis, ITT (defined as all those randomized into the study) will be used. Continuous variables will be expressed as mean and standard deviation; categorical variables expressed as absolute numbers and percentages. Baseline variables will be compared with an independent t-test (two tailed) after performing Levene's test for equality of variances in all normally distributed continuous variables and the Mann-Whitney test (two-tailed) in all not normally distributed variables. Categorical variables will be tested with two-sided Fisher's exact test. An analysis of variance (ANOVA) model with treatment as the main effect will be used to compare the treatment effect of rivaroxaban and warfarin treatment

strategies. For all measures, the analysis of covariance (ANCOVA) model controlling for baseline demographics and baseline CACS values will be performed. Treatment groups also will be compared with respect to incidence rates of adverse events, laboratory abnormalities, bleeding rates, and concomitant medication use. Measurements and change from baseline in coronary artery calcium scores, vital signs (blood pressure and pulse rate), continuous laboratory variables and compliance values will be summarized using descriptive statistics (mean, standard deviation, minimum, median and maximum) by treatment groups and visit. If the interaction of treatment by baseline laboratory values or CACS is significant at the 0.10 level or below, the nature of the interaction will be further explored. Spearman's rank correlation coefficient will be used for testing correlation between the mean Agatston score. All parameters showing a significant univariate relation with an increased coronary Agatston score and those representing a plausible mechanism in terms of calcification [age, VKA duration, left atrium (LA) diameter, statins, angiotensin-converting enzyme (ACE)-inhibitors] will be included as covariates in a logistic regression model (retention level set at 0.1), odds ratios and 95% confidence intervals (CIs) calculated, and results checked for interaction.

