Statistical analysis will be performed with SPSS statistical software (SPSS, Inc. release 18.0) and statistical significance assumed for  $P < 0.05$ . The primary and secondary efficacy analyses will include all patients who undergo randomization (intention-to-treat population) and include all events from the time of randomization until the end of the study. The analyses of bleeding events will include all patients who receive at least one dose of a study drug and included all events from the time the first dose of a study drug was received until 2 days after the last dose is received.

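### The logistic model of an increased Agatston score selects its covariates on the trial's own data, prunes them at P 0.1 and reports ordinary 95% confidence intervals, with the outcome undefined and the randomised arm not required

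*Combined protocol and SAP*

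**What the plan says.** The model is described at the end of the main paragraph under Statistical analysis (section 13).

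- **Entry by significance:** "All parameters showing a significant univariate relation with an increased coronary Agatston score".
- **Entry by naming:** "those representing a plausible mechanism in terms of calcification [age, VKA duration, left atrium (LA) diameter, statins, angiotensin-converting enzyme (ACE)-inhibitors".
- **Pruning:** both groups "will be included as covariates in a logistic regression model (retention level set at 0.1").
- **Output:** "odds ratios and 95% confidence intervals (CIs) calculated, and results checked for interaction". No allowance for selection is described.
- **Significance level:** "Statistical analysis will be performed with SPSS statistical software (SPSS, Inc. release 18.0) and statistical significance assumed for" P < 0.05. No separate level is given for the univariate step.

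The section gives no cut-off or time point for an increased score. It does not label the model primary, secondary or exploratory. Neither randomised arm nor baseline CAC is among the named covariates. Treatment is compared elsewhere in the same section: "An analysis of variance (ANOVA) model with treatment as the main effect will be used to compare the treatment effect", followed by an ANCOVA on baseline demographics and baseline CAC. Eligibility requires "Minimum CAC score of 10".

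**The concern.** Three things look wrong.

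First, the same patients are used to choose the covariates and to estimate them. A term is reported only if its estimate happened to be large relative to its standard error, so the printed interval no longer has its stated coverage and the odds ratio is pushed away from 1.

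Second, the outcome is open. Every patient enters with a CAC score of at least 10, so an increased score cannot mean present versus absent at baseline. It could mean any rise over the year, a rise beyond a threshold, or a high score at one visit. These readings give very different case counts, and a choice made after seeing the data is a free analytic choice.

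Third, in a randomised trial a model of calcification should hold the arm fixed. Here the arm enters only if it passes the univariate step.

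At stake is a published list of predictors of calcification with overstated odds ratios and intervals that are too optimistic.

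**Working it through.** The plan gives no sample size, event count or power for this model, so there is no figure of its own to reproduce.

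**1. What the selection rule implies by arithmetic.** Take a covariate with no effect, with the 0.1 rule applied to named and screened terms alike.
- Chance that at least one of five independent null named covariates survives: 1 − 0.9^5 = 1 − 0.590 = 41%.
- A null term is kept when P ≤ 0.10, and its 95% interval contains the truth only when P > 0.05. Coverage given retention is therefore about (0.10 − 0.05)/0.10 = 50%.
- A screened term must first reach univariate P < 0.05. Its interval can contain the null only if its P value rises above 0.05 in the joint model, so coverage is lower still.

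**2. Simulation.** From the documents: N = 100 (expected for final analysis) or 120 (enrolment), five named candidates, retention at 0.1, and the general 0.05 level used for the screen. Assumed: 10 extra candidates, pairwise correlation 0.2, 30% or 50% cases, and the log odds ratios shown. There were 1,500 data sets per setting, with backward elimination and Wald intervals.

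| Term, given that it is retained | Coverage of the 95% CI | Mean estimate |
|---|---|---|
| Named, all covariates null | 41% to 55% | – |
| Screened, all covariates null | 16% to 25% | – |
| Named, log OR 0.3 per SD | 88% to 92% | 0.54 to 0.62 |
| Named, log OR 0.7 per SD | 95% to 97% | 0.78 to 0.87 |
| Five named terms fixed, no selection | 93% to 96% | – |

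- The weak effect is inflated by 0.54/0.3 = 1.8 to 0.62/0.3 = 2.1 times; the strong one by 0.78/0.7 = 1.1 to 0.87/0.7 = 1.2 times.
- With everything null, 58% to 61% of final models kept at least one covariate. Further null runs at n = 100 gave about 40% with the named five alone and 61% to 78% with 10 to 20 extra candidates. Screened-term coverage in those runs was 7% to 16%.
- When some named covariates had real effects, 48% to 52% of models still kept a null one. Coverage for a screened null term was then 32% to 55%.

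**3. Treatment arm.** With 50 per arm and the arm entering only at univariate P < 0.05:
- At a true odds ratio of 1.5 it enters 19% of the time. When it does, the mean odds ratio is 2.7 and coverage is 86%.
- At a true odds ratio of 2.0 it enters 42% of the time, with mean odds ratio 3.0 and coverage 95%.
- Always in the model, its coverage is 94% to 95%.

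**4. Case counts if an increased score means any rise.** Under normality, the share rising in an arm is Φ(mean/SD). Average the two arms at 50 each.

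| Source of the percentage changes | Arm shares | Overall | Non-cases per 100 |
|---|---|---|---|
| Sample Size Estimation: 27.2 ± 9.5, 7.5 ± 4 | Φ(2.86) = 99.8%, Φ(1.88) = 97.0% | 98.4% | 1.6 |
| CAC and Progression, 23-patient garlic-extract trial: 22.2 ± 18.5, 7.5 ± 9.4 | Φ(1.20) = 88.5%, Φ(0.80) = 78.8% | 83.6% | 16.4 |
| CAC and Progression, statin cohort (volume score): 52 ± 36, 5 ± 28 | Φ(1.44) = 92.6%, Φ(0.18) = 57.1% | 74.8% | 25.2 |

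In the first row the chance of fewer than three non-cases is 78%, and no model with five or more covariates can sensibly be fitted. In the second row, 16.4/5 is about three non-cases per named covariate.

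**5. Data collection.** Age, statins and ACE inhibitors fall under the demographics and current medications collected at baseline (Study Design). Of "VKA duration, left atrium (LA) diameter, statins", neither LA diameter nor VKA duration is expressly listed there or among the CT variables in section 8.

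**The case against.** The strongest reply is that nothing important rests on this model. It is tied to no endpoint, sample size or decision rule. The primary endpoint is continuous percentage change, and treatment is tested by ANOVA and ANCOVA. That stands: the primary comparison is not affected.

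Three stronger readings are tempting, and the documents do not support them.

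- **The model omits the randomised arm.** The entry rule covers any univariately significant parameter, which does not exclude the arm. Under the planning figures, if an increased score meant a rise above 10%, above 15% or above the median, the arm would pass a Fisher screen at 0.05 in essentially every simulated trial. If it meant any rise, the arm would pass in only 0.7%. The accurate criticism is that the arm is not forced in.
- **The intervals are invalid throughout.** The severe losses apply to null covariates; strong effects keep their coverage. An all-null world also sits badly with the plan's own background, where age and VKA treatment were independently related to calcium score in an observational AF cohort. The five named covariates do not depend on the univariate screen to enter.
- **The plan's own figures leave almost no non-cases.** That needs both the any-rise reading and the narrow SDs in the sample-size section. The wider SDs elsewhere in the protocol leave about 16 to 25 non-cases per 100.

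The number of extra candidates, their correlation and the case share are assumptions. They move the figures but not the direction: the 41% and 50% results in the first step need no extra candidates.

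**Conclusion.** The concern holds for a secondary risk-factor model. As written, it will report intervals well below nominal coverage for covariates with no effect: about 50% for named terms and under 25% for screened terms when all covariates are null. Weak effects will be reported at roughly twice their size. Coverage for strong effects is close to nominal, with modest inflation. A false predictor survives in about 40% of all-null models from the named five alone, and in about 60% to 78% if 10 to 20 further candidates are screened.

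These figures assume a 0.05 univariate screen and a 0.1 rule that can drop named terms too, which is how the sentence reads. If the named five were exempt from pruning, the loss would fall mainly on the screened terms.

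Whether the model can be estimated at all depends on a definition the plan does not give: about 98% of patients are cases on one reading and set of SDs, and about 84% with wider SDs. The wording should be corrected before the analysis; the trial's treatment conclusion does not depend on it.

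**What to change.** - Remove the univariate screen and the 0.1 retention rule.
- Prespecify a fixed covariate list limited to variables the trial records, with randomised arm and baseline CAC always in the model. Age, statin use and ACE-inhibitor use qualify.
- Confirm that VKA duration is recorded before keeping it. Remove LA diameter unless it is already recorded; adding it as a new measurement would not be a wording change.
- Preferably model continuous CAC change linearly, as the log ratio or the percentage change defined under Sample Size Estimation. This overlaps with the planned ANCOVA but adds the risk-factor covariates. If a logistic model is kept, fix the cut-off and time point for an increased score in advance.
- Label the model exploratory.

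The cost is SAP wording only. The downside is fewer significant predictors to report.

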### Sample Size

**Sample Size Estimation.** Sample sizes for each efficacy area have been calculated assuming performance of two-sided 0.05 level tests and 90% power for the primary endpoint and >85% power for the secondary endpoint to detect differences considered clinically meaningful and plausible based on prior studies. We have based sample sizes on at least 90% power in all end points because false negatives could lead to abandoning further study of a treatment that could have a major positive impact on myocardial infarction in this population. The primary endpoint is progression of atherosclerosis after 1 year of treatment with warfarin compared to rivaroxaban as measured by the annualized relative change in the coronary calcium score, as assessed by the Agatston score. The primary endpoint will be the percentage change in CAC from the baseline, which was calculated as follows:  $(CAC \text{ score at 1 year} - CAC \text{ score at baseline}) / CAC \text{ score at baseline} \times 100$ . From multiple 1 year randomized studies in [name] lab, the mean annualized relative change in the Agatston calcium score was  $27.2 \pm 9.5\%$  and on pilot-treatment group, we observed an average change of  $7.5 \pm 4\%$ . Given a 19.7 % annual change difference (27.2% vs. 7.5%) between two groups was observed from primary data, the trial requires 100 in total (50 patients per arm) to attain power of 90% to detect the effect size according to a two-tailed two-sample t-test at a significance level 0.05 (see figure). If we consider the secondary

endpoint (noncalcified plaque volume change), we will have >85% power without drop-off at a two-tailed significance level 0.05 with 120 subjects.

The secondary endpoint is noncalcified plaque volume, using cardiac CTA. Cardiac CTA has been used successfully by [name] to measure progression of atherosclerosis (30-32). In one relevant study, the mean annualized relative change in the non-calcified plaque volume among 62 subjects given statin was -0.037 with a standard deviation of 0.351. This secondary comparison has power of 0.80 to detect an effect size of 0.5, the mean difference in the annualized relative change in the non-calcified plaque volume between the rivaroxaban and warfarin, according to a two sample t-test at a two-tailed significance level 0.05.

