### **Study Rationale**

The OVERALL HYPOTHESIS of this study is that use of rivaroxaban will slow progression of vascular calcification and coronary atherosclerosis as compared to warfarin therapy in patients with AFIB.

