#### **4. INVESTIGATIONAL PLAN AND STUDY DESIGN**

We propose a randomized, open label trial, to compare Rivaroxaban 20 mg oral once daily with food to warfarin (target international normalized ratio, 2.0 to 3.0) in patients with non-valvular atrial fibrillation. The primary endpoint will be CAC progression and key secondary objectives will be progression of total plaque, and development of new vulnerable plaques. Patients will be educated to maintain a low cholesterol diet through education to patients as well as medication compliance.

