*2b3b. Plaque evaluation.* Plaque will be evaluated from both axial source images and multiplanar reconstruction images of the long axis at each site of the coronary arteries. CP will be defined as any structure with a density greater than the contrast-enhanced lumen that could be visualized separately from the lumen, which could be assigned to the coronary artery wall, and that could be identified in at least two independent planes. NCP will be defined as any discernible structure that could be clearly assignable to the vessel wall, which had a CT density less than the contrast-enhanced coronary lumen but greater than the surrounding connective tissue, and that could be identified in at least two independent planes (1). Each coronary segment (15 AHA standardized coronary segments) will be classified as either normal, containing NCP, containing MP with either predominantly NCP (<50% of plaque area occupied by calcium) or containing CP.

Reviewer will independently evaluate the contrast-enhanced scans by assessment of the axial slices of multiplanar reformations and of three thin-slab maximum intensity projections.

Percentage of coronary arterial stenosis will be estimated on a cross-sectional image obtained from reconstruction of standardized coronary segments. Stenosis will be evaluated in a scale of 0-4: 0 (normal segment without stenosis or plaque present), 1 (1% to 29% stenosis), 2 (30% to 49% stenosis), 3 (50-69% stenosis), and 4 ( $\geq 70\%$  stenosis). Segments with diameter  $<1.5$  mm will be graded as small and therefore unable to evaluate for stenosis. Segment Stenosis Score" (SSS) will be determined by summing the number of evaluable coronary segments with individual stenosis scores (maximum score = 60 (score of 4 for all 15 segments)).

*2b3c. Plaque Composition.* The presence of noncalcified atherosclerotic plaque tissue will be defined as any discernible structure in the coronary artery wall with a CT density less than the contrast enhanced coronary lumen but greater than the surrounding connective tissue.

Measurements will be obtained from manually traced regions of interests encompassing the noncalcified plaque proportions.

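### The powered secondary endpoint, noncalcified plaque volume, can be pushed in opposite directions by the two benefits the trial hypothesises, and the plan has no rule for reading it with total plaque

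*Combined protocol and SAP*

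**What the plan says.** - **Powered secondary endpoint.** Section 13, Sample Size: "The secondary endpoint is noncalcified plaque volume, using cardiac CTA". That paragraph introduces CT angiography (CTA) as a way of measuring atherosclerosis progression. It gives two power figures: "we will have >85% power without drop-off at a two-tailed significance level 0.05 with 120 subjects", and "This secondary comparison has power of 0.80 to detect an effect size of 0.5, the mean difference in the annualized relative change".
- **Planning data.** The only NCP figures are a mean annualised relative change that "among 62 subjects given statin was -0.037 with a standard deviation of 0.351". No NCP value is given for warfarin or rivaroxaban, and no expected sign for the difference.
- **Key secondary objectives.** Section 4, Investigational Plan: "key secondary objectives will be progression of total plaque, and development of new vulnerable plaques". NCP is not named there.
- **Definition.** Section 8, 2b3b, takes CP as wall structure denser than the contrast-filled lumen, and NCP as structure "which had a CT density less than the contrast-enhanced coronary lumen but greater than the surrounding connective tissue".
- **Hypothesis.** Study Rationale: "use of rivaroxaban will slow progression of vascular calcification and coronary atherosclerosis as compared to warfarin therapy". Objective 2 says only that rivaroxaban will modify plaque, without a direction for NCP.
- **Data collected.** The Section 8 list includes total, noncalcified and calcified plaque volume and low-attenuation plaque.

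**The concern.** The Background argues that vitamin K antagonists promote calcification, including calcification within plaque in the cited mouse experiment. Under a density definition, plaque that calcifies far enough leaves NCP and enters CP, even if the total amount of plaque is unchanged. Less calcification on rivaroxaban, taken by itself, would then leave more NCP in that arm. Less plaque formation on rivaroxaban would leave less. Both are hypothesised benefits, and an NCP difference shows only their net effect.

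Two errors become possible. A real slowing of atherosclerosis may go undetected because less calcification offsets it. Or lower NCP on warfarin may be described as regression when the tissue has merely calcified. Neither the Secondary Endpoints list nor Section 13 says how a rise or fall in NCP is to be read beside CP and total plaque. The reading could therefore be chosen after the direction is known. This matters because the closing section intends the results to support an outcome trial.

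**Working it through.** **1. The plan's own power figures.** Inputs from the Sample Size section: effect size d = 0.5, two-sided alpha 0.05, 120 subjects (60 per arm). The Study Design section expects at least 100 evaluable (50 per arm).

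Power = Φ(d × √(n/2) − 1.96)

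- 60 per arm: 0.5 × √30 = 2.739; Φ(0.779) = 78.2% (t-test 77.5%).
- 50 per arm: 0.5 × √25 = 2.5; Φ(0.54) = 70.5% (t-test 69.7%).

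The 0.80 is reached only approximately, at 120 subjects. The figure above 85% is not reached; it needs 72 to 73 per arm. A one-sided 5% test would give 86.3% at 60 per arm and 80.4% at 50 per arm, but the text says two-tailed. If 0.5 is read as a raw difference with SD 0.351, power exceeds 99.9%, which matches neither figure.

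**2. Size of the calcification shift.** From the documents: calcium growth of 27.2% versus 7.5%, a difference of 0.197, and NCP SD 0.351. Assumed, because the documents give no figures: CP volume grows in step with the calcium score; r is the baseline CP:NCP volume ratio; f is the fraction of the extra calcium that replaces NCP.

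NCP excess on rivaroxaban = 0.197 × r × f; in SD units, divide by 0.351.

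| r | f = 0.5 | f = 1.0 |
|---|---|---|
| 0.25 | 0.025 (0.07 SD) | 0.049 (0.14 SD) |
| 0.5 | 0.049 (0.14 SD) | 0.099 (0.28 SD) |
| 1.0 | 0.099 (0.28 SD) | 0.197 (0.56 SD) |

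At r = 0.1 and f = 1 the shift is 0.0197, or 0.06 SD. With no difference in plaque formation and 60 per arm, the chance of significantly higher NCP on rivaroxaban is about 12% at 0.14 SD, 34% at 0.28 SD and 87% at 0.56 SD.

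**3. Masking.** Suppose slower plaque formation alone lowers NCP on rivaroxaban by 0.5 × 0.351 = 0.1755. With 60 per arm the standard error is 0.351 × √(2/60) = 0.0641.

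| Share of the effect offset by less calcification | Net NCP difference | Chance of significantly lower NCP | Chance of significantly higher NCP |
|---|---|---|---|
| 0% | −0.176 | 78% | about 0% |
| 25% | −0.132 | 54% | about 0% |
| 50% | −0.088 | 28% | about 0% |
| 100% | 0 | 2.5% | 2.5% |
| 150% | +0.088 | about 0% | 28% |

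Against a 0.5 SD benefit, the step 2 shifts are offsets of 0.07/0.5 = 14% to 0.56/0.5 = 112%. Only the corner r = 1, f = 1 exceeds 100%.

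**4. Does a joint reading separate the two processes?** Let c be the extra calcified volume on warfarin, and a the reduction in soft plaque from slower formation on rivaroxaban. Differences are rivaroxaban minus warfarin:

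- CP: −c
- NCP: +f × c − a
- Total: −(1 − f) × c − a

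If a = 0, the NCP difference is zero or positive and the total difference is zero or negative. The expected differences never share a sign, whatever f is. If a exceeds f × c, both are negative. If a is positive but smaller than f × c, NCP and total diverge and a real slowing is reported only as a change in composition, so the rule errs on the cautious side.

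**The case against.** A reader might infer that a calcification benefit would necessarily appear as worse NCP progression on rivaroxaban, or that the secondary result is uninterpretable. The documents support neither reading. The Study Rationale also hypothesises slower atherosclerosis, which lowers NCP, so reversal requires conversion to outweigh that effect. The documents contain no conversion data. The Background mentions calcification of the arterial media, which need not consume plaque, and reports other warfarin effects on plaque in mice. Five of the six cells in step 2 are 0.28 SD or less. Entry requires a calcium score of only 10, so low CP:NCP ratios cannot be excluded. Section 8 (2b2) describes a volume score independent of density, so the Agatston difference need not carry over to volume. All these points stand.

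It is also fair that total plaque and different plaque types are already listed and collected, that the test is two-sided, and that the study describes its sample size as exploratory. This limits the severity. It does not remove the gap: a two-sided test detects a difference but cannot say which process caused it, nor does it restore power lost to cancellation. Collecting the components is not the same as saying how they will be read.

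One further objection shapes the remedy. Total plaque includes CP, so whenever f is below 1 it falls on rivaroxaban from less calcification alone. Replacing NCP with total plaque would exchange one ambiguity for another.

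**Conclusion.** The point holds as an ambiguity of interpretation, together with a mismatch between sections. Section 13 powers NCP volume, Section 4 names total plaque, and no passage says how the two are read together. A calcification benefit could mask an NCP benefit and, in the extreme, reverse it; lower NCP on warfarin could be mistaken for regression.

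The size cannot be settled from the documents. The range of about 0.07 to 0.56 SD rests on three assumptions: CP volume tracking the calcium score, replacement of 50-100%, and CP:NCP ratios of 0.25 to 1.0. Lower ratios or lower replacement make it smaller. Masking does not need the extreme: offsetting a quarter of a 0.5 SD benefit lowers power from 78% to 54%. Severity is low, because the endpoint is secondary and the data needed to interpret it are already planned.

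**What to change.** Reconcile the Sample Size section with the Investigational Plan, and add to Section 13 wording such as: *Changes in total, noncalcified and calcified plaque volume will be analysed and reported together. Slower or faster progression of atherosclerosis will be concluded only if noncalcified and total plaque volume differ between arms in the same direction. If they diverge, the finding will be reported as a difference in plaque composition.*

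Neither NCP alone nor total plaque alone should carry the conclusion. The section should also say what counts as a difference. Requiring both confidence intervals to exclude zero on the same side is safer than comparing the signs of point estimates: at f = 0 or f = 1 one of the expected differences is zero, and its estimate could fall either way by chance.

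Cost: protocol and SAP wording, with no new scans or measurements. The secondary conclusion becomes somewhat more conservative. The power statement must be restated: for NCP at effect size 0.5, about 78% with 60 per arm and 70% with 50 per arm, two-sided. The documents give no SD for change in total plaque, so power for that measure, and for the joint rule, would have to be given as an assumption over a range.

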##### Study Design:

- a. Design. The study will be a single-center, randomized, open label comparison of Rivaroxaban **20 mg once daily with food** compared to warfarin therapy (INR target 2-3) for 52 weeks on coronary calcium, coronary plaque composition and volume. One hundred ten eligible subjects will be enrolled using a 1:1 ratio. The sample size in this study is based on exploratory considerations.
- b. Randomization and Stratification. Subjects who meet the eligibility criteria will be randomly assigned to receive rivaroxaban or warfarin
- c. **Endpoint Measures**

Primary - Rate of change in coronary calcium

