##### 2. Secondary Endpoints

1. To assess incident plaque rates and quantitative changes in different plaque types in patients randomized to warfarin vs. rivaroxaban using CTA, 12 months after an initial evaluation.
2. Evaluation of plaque progression rates and incident plaque rates in subjects treated with warfarin vs. rivaroxaban. In that context, we will:
  - a. determine whether subjects treated with rivaroxaban display slower rates of progression compared to warfarin treated subjects, after control for all CV risk factors and demographics

[figure not shown]
The study design calls for the enrollment of 120 eligible subjects of diverse ethnic population. Given dropout rate, at least 100 patients should be available for final analysis at the conclusion of 52 week follow-up. Baseline examination will include the results of their demographic, coronary risk factor, lab tests, coronary calcium, as well as coronary plaque volume/composition. All participants will be educated on a low-cholesterol diet at entry to the study. Baseline information regarding risk factors for atherosclerotic cardiovascular disease (cigarette smoking status, systemic hypertension, family history of premature atherosclerosis, menopausal and hormone replacement status in women, sedentary lifestyle, current medications, chest pain questionnaire and measures of obesity) will be determined. After randomization, participants will return quarterly (3, 6, 9 and 12 months to assess compliance with medication, and receive an additional supply of medicine. At 52 weeks follow up, coronary calcium and coronary plaque volume/composition will be measured by readers blinded to the randomization and clinical activities, who are not aware of study-group assignments

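### Three unreconciled powers are given for non-calcified plaque volume, and the named two-sided t-test does not deliver the stated 0.80 at any planned sample size

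*Combined protocol and SAP*

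**What the plan says.** All the power claims are in section 13, under Sample Size. Four of them cover non-calcified plaque volume:

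- The opening sentence sets the targets as "two-sided 0.05 level tests and 90% power for the primary endpoint and >85% power for the secondary endpoint". It gives no effect size.
- The next sentence says "We have based sample sizes on at least 90% power in all end points because false negatives could lead to abandoning" further study of the treatment.
- After the primary calculation, on non-calcified plaque volume: "we will have >85% power without drop-off at a two-tailed significance level 0.05 with 120 subjects". Again there is no effect size.
- The last paragraph says "This secondary comparison has power of 0.80 to detect an effect size of 0.5, the mean difference in the annualized relative change" in non-calcified plaque volume, "according to a two sample t-test at a two-tailed significance level 0.05". Here there is an effect size but no sample size.

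The only variability figure for this endpoint comes from a previous study, where the mean annualised relative change "among 62 subjects given statin was -0.037 with a standard deviation of 0.351".

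The planned numbers are in section 4. Study Design says "One hundred ten eligible subjects will be enrolled using a 1:1 ratio". The text under Secondary Endpoints gives an enrolment of 120 and adds "Given dropout rate, at least 100 patients should be available for final analysis at the conclusion of 52 week follow-up". The synopsis also says 120.

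**The concern.** One comparison cannot have power of 0.80, more than 85% and at least 90% unless the sample size or the assumed effect changes from one claim to the next, and the text does not say that either does. The 0.5 is also ambiguous: a single clause calls it an effect size and a mean difference in annualised relative change, just after an SD on that raw scale. The two readings lead to very different designs.

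Plaque change is Objective 2, and non-calcified plaque volume is the only CT angiography measure with a power statement. If a reader cannot tell whether the design has about 70% or practically 100% power, a non-significant plaque result cannot be set against a known detectable difference. The plan itself gives the danger of false negatives as its reason for wanting 90%.

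**Working it through.** **Inputs.** Two-sample t-test, two-sided 0.05, effect 0.5, SD 0.351 (section 13, Sample Size). Allocation 1:1 (section 4, Study Design). Totals of 100, 110 and 120, that is n = 50, 55 and 60 per arm (section 4; 120 also in section 13).

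**Formula.** For standardised difference d and n per arm, the noncentrality is λ = d·√(n/2) with 2n − 2 degrees of freedom. Power is the probability that a noncentral t variable with these parameters lies beyond ±t(0.975; 2n − 2).

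**Step 1: try to reproduce 0.80, taking 0.5 as standardised.**

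| Total | n per arm | λ | Critical t | Two-sided power |
|---|---|---|---|---|
| 100 | 50 | 0.5·√25 = 2.500 | 1.984 | 69.7% |
| 110 | 55 | 0.5·√27.5 = 2.622 | 1.982 | 73.8% |
| 120 | 60 | 0.5·√30 = 2.739 | 1.980 | 77.5% |

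The 0.80 is not reproduced. It is 10.3 points too high at 100 and 2.5 points too high at 120. The normal approximation gives 70.5%, 74.6% and 78.2%. Its value at 120 is near 0.80, but it is not the named test and does not reach 85%.

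**Step 2: sample size needed for each stated power at d = 0.5, two-sided t-test.** For 80%, 64 per arm (128 in total). For 85%, 73 per arm (146). For 90%, 86 per arm (172); 85 per arm falls just short at 89.99%.

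**Step 3: detectable d at the planned sizes, two-sided t-test.**

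| Total | 80% | 85% | 90% |
|---|---|---|---|
| 100 | 0.566 | 0.605 | 0.655 |
| 120 | 0.516 | 0.552 | 0.597 |

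With SD 0.351, the 80% figure at 100 patients is 0.566 × 0.351 = 0.199 in annualised relative change.

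**Step 4: take 0.5 as a raw difference.** d = 0.5/0.351 = 1.42. At 50 per arm λ = 1.4245 × 5 = 7.12, and power exceeds 99.9%. The 85% and 90% claims are then met with room to spare, and 0.80 is far too low. For a raw 0.5 to have 80% power at 100 patients, the SD would have to be 0.5/0.566 = 0.88, about 2.5 times the quoted value.

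**Step 5: look for a calculation behind the stated figures.** A one-sided 0.05 t-test with d = 0.5 gives 79.9% at 100 patients and 85.9% at 120. That matches both the 0.80 and the claim of more than 85%. They may be one one-sided calculation at two sample sizes, labelled two-tailed. This is an inference; the documents do not say it. It also leaves the 90% unexplained, because a one-sided test needs 140 patients for that.

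**The case against.** The strongest reply is that the size of the error is conditional. The plan never says that 0.5 is standardised, so the shortfalls hold on one reading only. This is correct, and it is why both readings are shown. But 0.80 fails on both.

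Second, a power above 85% is a lower bound that does not exclude 90%, and neither of those claims states an effect size. At 120 patients a d of 0.55 would justify the first and 0.60 the second. That also stands: applying 0.5 to those claims is an assumption. However, the plan states no larger effect, so the claims cannot be verified, and the 90% for all endpoints still sits beside an explicit 0.80 for one of them.

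Third, the 0.80 has no sample size attached, and at 120 it is only 2.5 points too high. That is fair, but 120 allows for no drop-out, and the plan expects to analyse about 100.

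Fourth, the study describes its sample size as exploratory and itself as a pilot. An adjusted analysis (ANCOVA is planned) could also have more power than the t-test, and a null result would in practice be read from its confidence interval. These points limit the consequence. They do not rescue specific power figures tied to a named test.

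**Conclusion.** The concern holds. Under the named two-sided t-test, the stated 0.80 is not obtained at 100, 110 or 120 patients on either reading of 0.5, and it conflicts with the claim of at least 90% for all endpoints.

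On the standardised reading, power is 69.7% to 77.5%. If the same 0.5 is carried over, the claim of more than 85% is about 7.5 points too high at its own 120 patients, and 90% is not reached at any planned size. On the raw reading, power exceeds 99.9%, assuming that the SD from 62 statin-treated subjects applies to this population.

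The lack of reconciliation and the failure to reproduce 0.80 are certain. Which shortfall applies depends on the scale of 0.5, which only the original calculation can settle. The primary endpoint's sample size is not affected. This should be fixed.

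**What to change.** 1. Find the original calculation and confirm whether 0.5 is standardised or raw, and whether the test was one- or two-sided.
2. Replace all the power claims for the secondary endpoint (the 0.80, both claims of more than 85%, and the 90% for all endpoints) with one statement giving sample size, sidedness, effect scale and SD. If 0.5 is standardised, a suitable text is: *With 100 evaluable patients, a two-sided 0.05 t-test has 80% power for a standardised difference of 0.57 (0.20 in annualised relative change if the SD is 0.351) and 70% power for a difference of 0.5 SD.* If 0.5 is raw, say so and give the matching power (above 99.9% at SD 0.351).
3. Use one enrolment figure, since section 4 gives both 110 and 120.

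The cost is a check of the original calculation and a change of wording. No extra patients are needed and the primary analysis does not change. On the standardised reading, the sponsor has to accept a less favourable stated power: about 70% for 0.5 SD instead of 80% to 90%.
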